10.2 REPORTING OF ADVERSE EVENTS

The Investigator is responsible for assessing the relationship of the adverse event to the treatment, and the seriousness and expectedness of the adverse event at the time of occurrence. A medically qualified person appointed by the Sponsor will also assess this, once the Sponsor has been notified of an AE. All adverse events that occur during the trial will be documented on the supplied adverse event forms.

AEs/SAEs reported during the study, or SAEs reported within 30 days of the end of the study, should be followed to resolution of the AE/SAE or, within thirty days from the end of the study. A final assessment of the outcome will be made at that time.

Each AE will be categorized as "serious" or "not serious" based on the definition of an SAE. An SAE is defined as an AE resulting in at least one of the outcomes:

- Results in death
- Is life threatening (the subject is at immediate risk of dying from the adverse experience)

CELLUTOME™ IN VENOUS LEG

- Requires subject hospitalization or prolongs existing hospitalization
- Results in persistent or significant disability/incapacity
- Is a congenital anomaly/birth defect

Important medical events that may not result in death, be life-threatening, or require hospitalization may be considered a serious adverse device effect when, based upon appropriate medical judgment, they may jeopardize the subject or subject and may require medical or surgical intervention to prevent one of the outcomes listed in this definition.

10.3 ADVERSE EVENT SEVERITY ASSESSMENTS

The guidelines outlined in CTCAE v4 will be used for severity assessments. Note: the term “severe” is a measure of intensity and that a severe AE is not necessarily serious.

AE SEVERITY GRADING SCALE

Severity Grade	Description
Mild (1)	Awareness of sign, symptom, or event, but easily tolerated; does not interfere with usual daily activities or tasks.
Moderate (2)	Discomfort enough to cause interference with usual daily activity. It may warrant therapeutic intervention.
Severe (3)	Incapacitating; inability to perform usual activities and daily tasks; significantly affects clinical status; requires therapeutic intervention.
Life-threatening (4)	Emergency treatment required life-threatening, death.

10.4 ADVERSE EVENT CAUSALITY ASSESSMENTS

Adverse events will be assigned a relationship (causality) to the treatments. The Investigator will be responsible for determining the relationship between an AE and the treatment. The type of event, organ system affected, and timing of onset of the event will be factors in assessing the likelihood that an AE is related to the treatment. Relationship of AEs to study products will be classified as follows:

- Not Related: No relationship exists between the AE and the treatment. The event is attributed to a pre-existing medical condition or an intercurrent event unrelated to the study product.
- Possibly Related: Follows the treatment, but may have developed as a result of an underlying clinical condition or treatments/interventions unrelated to the study product.
- Probably Related: Follows the treatment, but is unlikely to have developed as a result of the subject’s underlying clinical condition or other treatment or other interventions.
- Definitely Related: Follows the treatment and physical evidence shows a convincing relationship to the treatment.

CELLUTOME™ IN VENOUS LEG

- Unknown: Follows the treatment, but unable to determine the relationship to the treatment.

11 SERIOUS ADVERSE EVENTS

A Serious Adverse Event (SAE) is any untoward medical incident that occurs during the course of the trial beginning after informed consent has been executed and extending until 30 days after the final study visit.

A SAE is defined as any AE that:

- Results in death
- Is life threatening (the subject is at immediate risk of dying from the adverse experience)
- Requires subject hospitalization or prolongs existing hospitalization
- Results in persistent or significant disability/incapacity
- Is a congenital anomaly/birth defect
- Important medical events that may not result in death, be life-threatening, or require hospitalization may be considered a serious adverse device effect when, based upon appropriate medical judgment, they may jeopardize the subject or subject and may require medical or surgical intervention to prevent one of the outcomes listed in this definition.

11.1 REPORTING OF SERIOUS ADVERSE EVENTS

The Investigator is required to report all SAEs that occur during the study. Once the Investigator becomes aware of an SAE, he/she must report the SAE to SerenaGroup® and the Project Lead within 24 hours of discovery:

Medical Monitor	[name] MD FACS [contact]
------------------------	---

A written SAE report must follow and must include a full description of the event and all supporting documentation available at the time (e.g., lab reports, electrocardiogram [ECG] reports, etc.). Additional follow-up information as it becomes available must be reported to the Sponsor.

The Investigator is also responsible for reporting all SAEs to the appropriate Institutional Review Board (IRB) in accordance with local laws and regulations. The Investigator is responsible for maintaining documentation in the study file that indicates the IRB has been properly notified.

11.2 SAE FOLLOW-UP

All SAEs will be monitored for a minimum of 30 days until they are resolved, have stabilized, or are clearly determined to be due to a subject's stable or chronic condition or intercurrent illness(es).

12 DIRECT ACCESS TO SOURCE DATA/DOCUMENTATION

Subjects will be identified on CRFs by a unique subject identification number and on source documents by name and date of birth. No personal identifier will be used in any publication or communication used to support this research study. The subject identification number will be used if it becomes necessary to identify data specific to a single subject.

The monitors, auditors, personnel authorized by the Sponsor, the local IRB, and the FDA are eligible to review medical and research records related to this study as a part of their responsibility to protect human subjects in clinical research and will be given direct access to source data and documentation (e.g., medical charts/records, printouts etc.) for source data verification, provided that subject confidentiality is maintained in accordance with local requirements. Access to electronic medical records may be governed by institution policy and each site will be required ensure access while remaining compliant with institutional requirements.

13 QUALITY CONTROL AND QUALITY ASSURANCE

13.1 ACCEPTABILITY OF CASE REPORT FORMS

CRF must be completed for each subject who has signed an informed consent form. For subjects who are screen failures, this would be limited to the screen failure CRF page. All source documents and CRFs will be completed as soon as possible after the subject's visit.

13.2 MODIFICATION OF PROTOCOL

The Investigator will not modify or alter this protocol without first obtaining the concurrence of the Sponsor. Approval by the Investigator's IRB must also be obtained prior to implementation of the change, with two exceptions:

1. When necessary to eliminate apparent immediate hazard to the subject; or
2. When the modification does not involve the subject's participation in the trial.

An amendment may also require modification of the informed consent form. The Investigator will provide an approval letter for the amendment and revised informed consent form, if applicable, to the Sponsor. An amendment must be in writing and it must be dated by both the Sponsor and the Investigator. If necessary, the Sponsor will submit protocol amendments to FDA and other appropriate regulatory authorities and notify other Investigators using this protocol.

13.3 REPORTING PROTOCOL DEVIATIONS

The Investigator is obligated to follow the protocol without departure from the requirements written in the protocol. If the Investigator deviates from the protocol requirements, the Sponsor will make the determination as to whether the subject will continue in the study. The Sponsor also has the right to discontinue the subject for protocol violations. The IRB may also have to be contacted if safety to the subject or if the scientific soundness of the study is involved. All protocol deviations must be documented in the CRFs.

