6.4 SUBJECT COMPLETION AND WITHDRAWAL

SUBJECT COMPLETION

- A subject whose study ulcer has closed will be considered as having completed the study.
- A subject who completes the Treatment Phase will be considered as having completed the study.

SUBJECT PREMATURE WITHDRAWAL FROM THE STUDY

A subject who is randomized into the Treatment Period of the study but who does not complete the study through TV4 has prematurely discontinued.

All subjects have the right to withdraw at any point during treatment without prejudice. It will be documented whether or not each subject completed the clinical study. If for any subject, study treatment or observations were discontinued, the reason(s) will be recorded.

The Investigator can discontinue a subject at any time if it is considered medically necessary.

In addition, subjects WILL be withdrawn from the study, in consultation with the Medical Monitor and the Investigator, if any of the following are met:

- A subject is significantly non-compliant with the requirements of the protocol.
- A subject becomes pregnant (Note: the pregnancy will be followed up to term for safety follow-up. Relevant safety information collected after the study has completed will be reported as supplemental information.)
- A subject has revascularization surgery on the leg with the study (target) ulcer.
- A subject has a target ulcer wound bed that has exposed bone, tendon or fascia.
- The subject's study ulcer cannot be dressed with multi-layer compression.
- Two separate infections with no response to allowable treatments
- The subject's ulcer merges with an adjacent ulcer.

Premature withdrawal from the study MAY occur if:

- A subject is treated with a prohibited medication. This decision will be made by the Medical Monitor in conjunction with the Investigator as to whether premature withdrawal is warranted.

Every attempt should be made to collect follow-up information. The reason for treatment discontinuation or withdrawal from the study will be recorded in the source documents and on the appropriate page of the CRF.

Before a subject is identified as lost-to-follow up, the site should make all reasonable efforts to contact the subject. These attempts must be documented and should include at a minimum one phone call and one certified letter.

In the event that a subject is prematurely discontinued from the study at any time due to an adverse event of SAE, SAE procedures must be followed.

SCREEN FAILURES

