9.7 STATISTICAL METHODS

MISSING DATA

Missing data may be the result of missed visits, subjects lost to follow-up or who have died, or data not available (e.g., smoking status).

Missing primary endpoint data within 12 weeks from start of study will not be imputed for ITT populations as these will constitute right-censored data in the time to heal analysis. The last visit for which data are available will constitute the start of censoring (healing outcome). For secondary endpoints within 12 weeks from start of study, the last observation carried forward (LOCF) principle will be used for ITT populations.

For adjusted analyses of primary and secondary endpoints, missing data for covariates used to adjust analyses may be imputed in separate models when the missing data for each covariate is $\leq 30\%$ and it can be reasonably demonstrated that the missing data for each covariate are MCAR.

FINAL ANALYSIS

Analysis can be started when database lock for the trial is initiated. In regard to statistical modeling, the initial list of independent variables will be examined for correlation between pairs. In the event that

correlation (however calculated) exceeds 0.7, a selection will be made between the 2 variables to avoid possible issues of co linearity and variance inflation.

The following analysis will be conducted:

1. Flow chart (subjects)
2. Overall trial statistics (enrollment dates, site numbers, numbers of subjects)
3. Demographics between groups at baseline (no statistical testing but identification of likely trial imbalances)
4. Count of subjects in each group
5. Primary endpoints within 6 and 12 weeks (time to heal; previously defined by groups) will be analyzed by Kaplan-Meier and log rank test (unadjusted); and then Cox regression to adjust for the following variables (with and without covariate imputation):

- Site
- Year enrolled (if trial lasts 2 years or more)
- Treatment group
- Initial area at randomization (cm²)
- Initial wound depth (cm)
- Age of wound at enrollment (days)
- Smoking status
- Prior VLU
- Pain score at randomization
- Patient age
- Gender
- Ethnicity/race
- VCS score
- Diabetes
- Patient on pain medications
- Smoking status
- BMI
- Infection episodes

6. Secondary endpoints will be analyzed as follows:

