15.2 CLINICAL DATA MANAGEMENT

The Sponsor will be responsible for the processing and quality control of the data. Data management will be carried out as described in the Sponsor's standard operating procedures (SOPs) for clinical studies.

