17.12 PROTOCOL ADHERENCE/VIOLATIONS/DEVIATIONS/SERIOUS BREACHES

A breach of GCP and/or protocol is defined as **serious** when it is likely to affect to a significant degree:

- The safety or physical or mental integrity of the subjects of the trial; or the scientific value of the trial.

A protocol violation is a serious failure to comply with the study protocol and may result in the exclusion of the subject from the study.

SerenaGroup® (sponsor) shall review all protocol violations/deviations submitted by the site and/or monitor and documented in the monitoring report. At each monitoring visit the site monitor will verify the following:

- Protocol Adherence.
- Protocol violations/deviations (e.g. missing procedures or evaluations outside of scheduled visits) – these should be recorded in the source document and discussed with the site to prevent future occurrence.
- Document protocol violations and deviations in the monitoring report (which is filed in the TMF) and Investigator Follow-up Visit letter (which is filed in the TMF and ISF).
- Verify the Independent Ethics Committee (IEC) reporting requirements on Protocol Violations and document such requirements in the monitoring report and follow up visit letter and file in TMF and ISF.

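### Protocol 13.3 lets the sponsor decide, without criteria or stated blinding, whether a randomised subject stays in the study after an investigator's deviation, and no closure assessments are scheduled after a removal.

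*Combined protocol and SAP*

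**What the plan says.** Section 13.3 contains two sponsor powers. The first is triggered by the investigator's conduct: "If the Investigator deviates from the protocol requirements, the Sponsor will make the determination as to whether the subject will continue in the study". The second is general: "The Sponsor also has the right to discontinue the subject for protocol violations". Neither has a criterion, a time limit or an independent decision-maker.

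Section 17.12 adds: "A protocol violation is a serious failure to comply with the study protocol and may result in the exclusion of the subject from the study". It also says that the sponsor "shall review all protocol violations/deviations submitted by the site and/or monitor and documented in the monitoring report". Section 6.4 lists among the reasons for mandatory withdrawal: "A subject is significantly non-compliant with the requirements of the protocol". The same section asks that follow-up information be sought after a withdrawal and that the reason be recorded.

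On access to data, the title describes the trial as open-label. Section 15.2 says: "The Sponsor will be responsible for the processing and quality control of the data". Section 17.2 provides for remote access to case report forms. In section 6.3 only the closure assessment is assigned to a blinded observer.

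On analysis, SAP 9.7 censors missing primary data from the last visit with data. For the rest: "For secondary endpoints within 12 weeks from start of study, the last observation carried forward (LOCF) principle will be used for ITT populations". SAP 9.6 names an ITT population but does not define it as all randomised subjects followed to week 12. It also defines a per-protocol population that leaves out any subject with a violation.

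**The concern.** A deviation by the investigator says nothing about the subject's willingness or safety. Ending the subject's participation for that reason discards outcomes that the weekly visits would have captured. The per-protocol population already deals with deviations, so removal from the study adds nothing to the analysis.

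The decision is discretionary, and no text keeps the decision-maker blind to arm or progress. If the discretion were exercised more often for slow-healing ulcers in one arm, the censoring would be informative. The intent-to-treat log-rank test would then favour that arm. For the closure proportion, an ulcer open at removal stays open by carry-forward. Neither loss can be repaired at analysis, because the outcomes were never recorded.

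**Working it through.** **1. The plan's own figure.** Inputs from SAP 9.3: 113 control and 112 treatment subjects, 50% healed on control, hazard ratio 1.74, 12 weeks, dropout 0.033 and 0.0083 per week.
- Hazards: control ln2/12 = 0.0578 per week; treatment 1.74 × 0.0578 = 0.1005.
- Expected events per arm: n × λ/(λ+γ) × (1 − exp(−12(λ+γ))), with γ = −ln(1 − weekly dropout). This gives 47.6 + 75.4 = 123.0.
- Schoenfeld power: Φ(√123.0 × ln(1.74)/2 − 1.96) = Φ(1.11) = 86.7%. A Lakatos calculation with weekly intervals gives 86.0%.

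The stated 86.1% reproduces and is not in dispute.

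**2. What happens to a removed subject.** Reading 13.3, 6.3, 6.4 and 9.7 together:
- 13.3 ends participation in the study, not only study treatment.
- 6.3 schedules closure assessments for subjects in the Treatment Phase, and none for a discontinued subject.
- 6.4 asks for follow-up information but sets no visit and no closure assessment.
- 9.7 censors for time to heal and carries forward for the closure proportion.

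**3. Effect on time to heal.** The documents give no removal rate, so the rates here are assumptions. The model has no treatment effect, arms as randomised (112 v 113), weekly assessment, 50% healed by week 12, and unequal healing propensity (gamma frailty variance 1 to 2). Removals are at week 3. The result is the chance that the log-rank Z exceeds 1.96 in favour of the graft (nominal 2.5%).

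| Removal | False graft win |
|---|---|
| 6 of 112 (5%), Group 1A only, slower half of open ulcers | about 4% |
| 11 of 112 (10%), Group 1A only, slower half | about 5-6% |
| 10%, slower half, both arms | 2.6-2.7% |
| 10%, Group 1A only, at random (variance 1) | 2.9% |

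The spurious hazard ratio is about 1.03-1.04 for 5% and 1.07 for 10%.

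A second model was also run: half the ulcers slow (20% healed at 12 weeks), half fast (80%), removal at week 4. With about 5 and 10 slow Group 1A subjects removed, it gives 3.3% and 4.6%, against 2.4% with none removed. Random removal of 10-20% of open ulcers in both arms leaves the two-sided error at about 5%.

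**4. Scale against the plan's dropout.** For Group 1A, 1 − (1 − 0.0083)^12 = 9.5%, and 0.095 × 112 = 10.7 subjects. The 5% row fits inside that allowance. The 10% row uses all of it.

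**5. Effect on the closure proportion.** This uses the hazards from step 1, 11 subjects removed at week 4 regardless of progress, and open ulcers carried forward as not healed.
- Treatment without removal: 1 − exp(−0.1005 × 12) = 70.1%. Power against 50% is 87%.
- Later closures among removed Group 1A subjects: 1 − exp(−0.1005 × 8) = 0.55; 11 × 0.55 = 6.1 closures lost. The proportion becomes 64.6%.
- Removed from Group 1A only: power about 60%. Removed 11 from each arm: about 79%.

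Most of the fall to 60% therefore comes from the assumption that every removal is in one arm.

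**The case against.** The strongest reply is that 13.3 is a general conduct clause and that the surrounding text limits it. Much of that stands.

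- **Sponsor knowledge.** A reader might infer that the sponsor knows arm and outcome when deciding. No sentence says so. It follows only by inference from the open-label design, sponsor data processing and remote access to case report forms. SAP 9.6 speaks of unblinding interim analyses, which leaves the position unclear. The documents support only that no blinding is stated.
- **Reach.** A reader might infer that almost any subject could be excluded, because 17.12 mentions missed procedures and off-schedule evaluations. But 17.12 ties exclusion to a serious failure to comply. The minor items are to be recorded and discussed with the site. Only the first quoted sentence of 13.3 reaches ordinary deviations.
- **Visibility.** Section 6.4 asks for follow-up and recorded reasons, and SAP 9.7 requires withdrawals by group with reasons. Uneven removal would be seen, although the missing outcomes would not be recovered.
- **Size.** The inflated error rates need removals in one arm that are related to prognosis. A headline of 60% power for the closure proportion is not supported, for the reason in step 5.
- **Direction.** A reader might infer that the same removals push time to heal and closure in opposite directions. The two calculations use different removal patterns. Removing 10% of Group 1A as slow healers at week 3, with no treatment effect, loses only about 1-2 closures.
- **Comparison.** At 12 weeks the plan compares Group 1A with Group 2B, not the arms as randomised. The figures show the mechanism and do not give the operating characteristics of the planned 12-week tests.

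**Conclusion.** The gap is real and modest. As written, 13.3 allows a criterion-free removal with no stated blinding, and nothing schedules outcome assessment afterwards. If removals are related to both arm and prognosis, the intent-to-treat comparison is biased. On assumed removal of about 5-10% of Group 1A, all slow healers, at week 3, the one-sided false-win rate rises from 2.5% to about 4-6%. Under random or balanced removal it stays near nominal. These figures rest on assumed rates, an assumed spread of healing propensity and arms as randomised. The documents do not say how often 13.3 would be used, and nothing in them shows or implies intended selection. The point is a worthwhile, low-cost improvement.

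**What to change.** In 13.3 and 17.12, state that:
- a protocol deviation or violation is documented and does not by itself end outcome follow-up;
- the subject keeps the scheduled closure assessments to TV13 unless consent is withdrawn or a separate medical or safety withdrawal under 6.4 applies, and is analysed in the ITT population as randomised;
- deviations affect only per-protocol membership, settled before database lock without reference to arm or outcome.

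Cross-refer to the follow-up request in 6.4, and align the 6.4 non-compliance bullet for data collection only. The exception for 6.4 withdrawals is needed. A rule allowing only withdrawal of consent would contradict the other 6.4 bullets and the investigator's power to discontinue on medical grounds. Decisions on study treatment and safety are unchanged.

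The cost is a few sentences, and the visits are already scheduled. The downside is that subjects with deviations stay in the ITT set and may slightly dilute the effect; the per-protocol analysis shows the result without them.
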